5.3.1. Plasma Pharmacokinetic Parameters

Actual PK sampling times will be used in the derivation of plasma PK parameters.

If a PK parameter cannot be derived from a participant's concentration data, the parameter will be coded as NC (i.e. not calculated). (Note that NC values will not be generated beyond the day that a participant discontinues.)

In summary tables, statistics will be calculated by setting NC values to missing; and statistics will be presented for a particular group/analyte with ≥ 3 evaluable measurements. For statistical analyses (i.e. linear regression), PK parameters coded as NC will also be set to missing; and analyses will not be performed for a particular parameter if more than 50% of the data are NC.

If an individual participant has a known biased estimate of a plasma PK parameter (due for example to an unexpected event such as vomiting before all the compound is adequately absorbed in the body – within ~2 times the median Tmax after the dose of PF-06882961), this will be footnoted in summary tables and will not be included in the calculation of summary statistics or statistical analyses.

6. ANALYSES AND SUMMARIES

Unless otherwise stated, all analyses, summaries and listings will be produced by group (as outlined in Section 5), which would include all 5 groups in the same analysis/output.

6.1. Primary Endpoint(s)

6.1.1. C_{\max} , AUC_{inf} , AUC_{last} , fu for PF-06882961

6.1.1.1. Main Analysis

C_{\max} , AUC_{inf} (if data permit), AUC_{last} and fu will be listed, summarized descriptively and analyzed by group for participants in the PK parameter set (as defined in Section 4). Missing values will be handled as detailed in Section 5.3.1.

Linear regression will be used to characterize the potential relationship between appropriate PK parameters (CL/F , CL_u/F and CL_r) for PF-06882961 and renal function (eGFR as obtained on Day 1 and defined by the SCr-based CKD-Epi equation in Section 3.2.1), as described in Section 5.2.4, where the PK parameter will be the dependent variable in the separate models.

Plots of PK parameters (CL/F , CL_u/F and CL_r) for PF-06882961 versus renal function (eGFR as obtained on Day 1 and defined by the SCr-based CKD-Epi equation in Section 3.2.1) will be constructed. A regression line and 90% confidence region for the PK parameters and eGFR will be included if appropriate. Vertical lines for the renal function group cut-off values will also be presented on the plots. Different symbols will be used to identify participants from different renal function groups.

For exploratory purposes, these analyses and figures will additionally be carried out separately for each of the alternative two methods for calculating eGFR, as defined in Section 3.2.1.

A one-way analysis of variance (ANOVA) described in Section 5.2.3, that includes all 5 groups in the same model, will be used to compare the natural log transformed of C_{\max} , AUC_{inf} , AUC_{last} and fu of PF-06882961 separately, for each of the T2DM renal impairment groups (Test, Groups 3, 4, 5) to the T2DM normal renal function group (Reference, Group 2). Also, the T2DM normal renal function group (Test, Group 2) will be compared to the healthy normal renal group (Reference, Group 1).

For summary statistics and median or mean plots by sampling time, the nominal PK sampling time will be used. For individual participant plots by time, the actual PK sampling time will be used. The plasma PK parameters of PF-06882961 for each group will be summarized as specified in Table 7 below.

Table 7. Summary statistics to be produced for Plasma PK Parameters of PF-06882961

Parameter	Summary Statistics
-----------	--------------------

C_{\max} , AUC_{inf} (if data permit), AUC_{last} and fu	N, arithmetic mean, median, $cv\%$, standard deviation, minimum, maximum, geometric mean and geometric $cv\%$.
---	--

Supporting data from the estimation of $t_{1/2}$ will be listed by group: terminal phase rate constant (k_{el}); goodness of fit statistic from the log-linear regression (r^2); the percent of AUC_{inf} based on extrapolation ($AUC_{\text{extrap}\%}$); and the first, last, and number of time points used in the estimation of k_{el} . This data may be included in the clinical study report.

The following plot will be presented:

- Box and whisker plots for individual PK parameters (AUC_{inf} , AUC_{last} , C_{\max} and fu) will be constructed by group and overlaid with geometric means.

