As indicated in Table 1, the estimate of eGFR will be based on the SCr-based CKD-Epi equation:¹⁵

- $eGFR \text{ (mL/min/1.73m}^2\text{)} = 141 \times \min(\text{SCr} / \kappa, 1)^\alpha \times \max(\text{SCr} / \kappa, 1)^{-1.209} \times 0.993^{\text{Age}} \times 1.018 \text{ [if female]} \times 1.159 \text{ [if Black].}$

where:

- SCr is serum creatinine in mg/dL (based on the standardized assay);
- κ is 0.7 for females and 0.9 for males;
- α is -0.329 for females and -0.411 for males;
- Min indicates the minimum of SCr / κ or 1;
- Max indicates the maximum of SCr / κ or 1;
- Age is in years.

The eGFR value will be multiplied by each participant's ratio of BSA/1.73 to obtain the BSA-unnormalized eGFR value as shown below:

- $eGFR \text{ (mL/min)} = eGFR \text{ (mL/min/1.73m}^2\text{)} * [\text{BSA (m}^2\text{)} / 1.73].$

The BSA of an individual will be calculated using the following equation:¹⁶

$$\text{BSA (m}^2\text{)} = [\text{Weight(kg)}^{0.425} \times \text{Height(cm)}^{0.725}] \times 0.007184$$

Participants with T2DM and varying degrees of renal impairment (Groups 3-5) will be recruited and enrolled first. An average value for age and weight for these groups will be determined and participants in Groups 1-2 will be recruited to match the average demographics (at a minimum, age and weight, and as much as practically possible gender) across the pooled Groups 3-5. Recruitment for participants in Groups 1-2 may start when approximately 75% of total participants across Groups 3-5 (ie, approximately 17-18) have been dosed. Approval from the sponsor must be garnered **before** proceeding with dosing participants in Groups 1 and 2.

Refer to [Section 1.2](#) for study schema. For individual participants, the total duration of participation from the Screening Visit to the Follow-up Contact will be a minimum of approximately 5 weeks and a maximum of approximately 10 weeks.

Participants who discontinue from the study before completing all assessments may be replaced at the discretion of the investigator and sponsor.

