2.2. Study Design

This Phase 1, open-label, single-dose, parallel group, multi-site study will assess the effect of varying degrees of renal impairment on the PK, safety and tolerability of PF-06882961 after a single oral dose of 20 mg administered in a fed state.

Approximately 40 participants will be enrolled in the study. Refer to [Table 2](#) below for details of study groups. Due to the potential difficulty in recruiting T2DM patients with estimated glomerular filtration rate (eGFR) <30 mL/min, the number of participants to be enrolled in this group is flexible (6 to 8 participants).

This study will permit enrollment of 2-4 participants on dialysis, as part of the severe renal impairment group, to assist in recruitment of patients with more advanced renal impairment and to permit assessment of the PK of PF-06882961 in participants with the highest degree of renal impairment. Since PF-06882961 has a large unbound non-renal clearance and a large unbound volume of distribution, dialysis is not expected to significantly impact the clearance of PF-06882961 and therefore the dialysis clearance of PF-06882961 will not be characterized in this study. Thus, Day 1, per the schedule of activities, will occur in dialysis patients on a day in which dialysis is not administered.

Table 2. Study Groups

Group	Disease State	Renal Impairment	No. of Participants	eGFR^a (mL/min)
1	None (healthy)	None (Normal Renal Function)	8	≥90
2	T2DM	None (Normal Renal Function)	8	≥90
3	T2DM	Mild	8	60-89
4	T2DM	Moderate	8	30-59
5	T2DM	Severe	6-8 ^b	<30

*a. Estimate of eGFR based on the SCr-based CKD-Epi equation. The eGFR will be multiplied by each participant's ratio of BSA/1.73 to obtain the BSA-unnormalized eGFR value. The average of the 2 unnormalized eGFR values from S1 and S2 will be used for study enrollment and group placement. **Note:** participants on dialysis will be placed in Group 5 regardless of unnormalized eGFR from S1 and S2.*

[figure not shown]
b. This includes approximately 4 participants not on dialysis and 2-4 participants on dialysis.

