Screening will occur within 28 days of the first dose of study intervention on Day 1. All participants will provide informed consent and undergo Screening evaluations to determine their eligibility. All participants who are not on dialysis must have stable renal function to enter the study, defined as ≤25% difference between 2 measurements of BSA-unnormalized eGFR obtained from the 2 screening visits, S1 and S2 as listed in the schedule of activities. As indicated in Table 2, the estimate of eGFR will be based on the SCr-based CKD-Epi equation, defined in Section 3.2.1.

*Participants with T2DM and varying degrees of renal impairment (Groups 3-5) will be recruited and enrolled first. An average value for age and weight for these groups will be determined and participants in Groups 1-2 will be recruited to match the average demographics (at a minimum, age and weight, and as much as practically possible gender) across the pooled Groups 3-5. Recruitment for participants in Groups 1-2 may start when approximately 75% of total participants across Groups 3-5 (ie, approximately 17-18) have been dosed. Approval from the sponsor must be garnered **before** proceeding with dosing participants in Groups 1 and 2.*

Refer to Figure 1 for study schema.

Participants who discontinue from the study before completing all assessments may be replaced at the discretion of the investigator and sponsor.

Figure 1. Study Schema

*Screening period is \leq 28 days from dosing on Day 1.

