3.2. Secondary Endpoint(s)

3.2.1. Additional Plasma PK parameters of PF-06882961

- $C_{max,u}$, $AUC_{inf,u}$, $AUC_{last,u}$, CL/F , CL_u/F , V_z/F , $V_{z,u}/F$, T_{max} , $t_{1/2}$, as data permit

The plasma PK parameters for PF-06882961 in Table 4 will be determined using standard non-compartmental methods:

Table 4. Summary of Additional Plasma PK parameters of PF-06882961 to be calculated

Parameter	Analysis Scale	PF-06882961 20mg
CL/F^*	ln	A, D
V_z/F^*	ln	D
T_{max}	R	D
$t_{1/2}^*$	R	D

*=if data permits. Abbreviations: A = analyzed using a statistical model; D=displayed with descriptive statistics as outlined in [Table 8](#) in Section [6.2.1](#); ln=natural-log transformed; R=raw (untransformed).

The plasma PK parameters for unbound PF-06882961 will be calculated as described in Table 5:

Table 5. Summary of Plasma PK parameters of Unbound PF-06882961 to be calculated

Parameter	Method of Determination	Analysis Scale	PF-06882961 20 mg
$AUC_{last,u}$	$fu \times AUC_{last}$	ln	D
$AUC_{inf,u}^*$	$fu \times AUC_{inf}$	ln	D
$C_{max,u}$	$fu \times C_{max}$	ln	D
CL_u/F^*	$Dose/(AUC_{inf,u})$	ln	A, D
$V_{z,u}/F^*$	$Dose/(AUC_{inf,u} \times k_{el})$	ln	D

*=if data permits. Abbreviations: A = analyzed using a statistical model, D=displayed with descriptive statistics as outlined in [Table 8](#) in Section [6.2.1](#); ln=natural-log transformed, R=raw (untransformed).

For the linear regression analysis assessing the relationship between CL/F , CL_u/F and CL_r and eGFR, the primary equation for eGFR will be SCr-based:

CKD-Epi equation⁽¹⁾: $eGFR \text{ (mL/min/1.73m}^2\text{)} = 141 \times \min(\text{SCr } / \kappa, 1)^\alpha \times \max(\text{SCr } / \kappa, 1)^{-1.209} \times 0.993^{\text{Age}} \times 1.018 \text{ [if female]} \times 1.159 \text{ [if Black]}$

where:

- SCr is serum creatinine in mg/dL (based on the standardized assay)
- κ is 0.7 for females and 0.9 for males
- α is -0.329 for females and -0.411 for males
- min indicates the minimum of SCr / κ or 1
- max indicates the maximum of SCr / κ or 1
- Age is in years

Additional outputs will also be produced using the following alternative equations to calculate eGFR:

Cockcroft-Gault (CG)⁽²⁾: eGFR (ml/min/1.73 m²) = [(140-Age) \times Weight \times 0.85 if female]/(72 \times SCr)

Modification of Diet in Renal Disease (MDRD)⁽³⁾: eGFR (ml/min/1.73 m²) = 175 \times (SCr)^{-1.154} \times (Age)^{-0.203} \times (0.742 if female) \times (1.212 if black)

where:

- Age is in years
- Weight is in kg

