5.2.4. Linear Regression

Linear regression analysis will include eGFR as the explanatory variable, based on eGFR values obtained on Day 1 and will include only participants from the T2DM groups (Groups 2 to 5). Estimates of the slope and intercept, together with their precision (90% CIs), and the coefficient of determination will be obtained from the model. Example SAS code is given in [Appendix 1](#).

Additionally, as an exploratory analysis, the effect of weight, gender and age will be explored as additional covariate/factors in the models, as appropriate. This will be implemented by utilizing a stepwise linear regression approach, with model selection using Akaike's Information Criterion [AIC]). All the above covariates and factors will be considered (eGFR will be restricted to always remain in the model) and if the final model selected includes at least one of these additional covariates/factors, this additional model will be reported in addition to the main linear regression above. Example SAS code is given in [Appendix 1](#).

5.3. Methods to Manage Missing Data.

For the analysis of safety endpoints, the sponsor data standard rules for imputation will be applied.

In all PK data presentations (except listings) and CP-I, concentrations below the limit of quantification (BLQ) will be set to zero. In listings BLQ values will be reported as “<LLQ”, where LLQ will be replaced with the value for the lower limit of quantification.

In PK summary tables and plots of median profiles, statistics will be calculated having set concentrations to missing if one of the following cases is true:

1. A concentration has been collected as ND (i.e. not done) or NS (i.e. no sample),
2. A deviation in sampling time is of sufficient concern or a concentration has been flagged anomalous by the pharmacokineticist.

Note that summary statistics will not be presented at a particular time point if more than 50% of the data are missing.

Participants who experience events that may affect their PK profile (e.g. lack of compliance with dosing or vomiting) may be excluded from the PK analysis. At the discretion of the pharmacokineticist, a concentration value may also be excluded if the deviation in sampling time is of sufficient concern or if the concentration is anomalous for any other reason.

A full list of protocol deviations will be compiled and reviewed to identify major and minor deviations prior to database closure.

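### The clearance regressions and plots take eGFR per 1.73 m² with no BSA step, but the cut-off lines are in mL/min; the Cockcroft-Gault unit is also mislabelled

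*SAP*

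**What the plan says.** **Regression and plots.** SAP 6.1.1.1 regresses CL/F, CLu/F and CLr on renal function and plots them against it, taking "eGFR as obtained on Day 1 and defined by the SCr-based CKD-Epi equation in Section 3.2.1". SAP 3.2.1 introduces the equation for this regression, stating that "the primary equation for eGFR will be SCr-based", and prints CKD-EPI in mL/min/1.73 m². No BSA multiplication or BSA formula follows. SAP 5.2.4 adds only this: "Linear regression analysis will include eGFR as the explanatory variable, based on eGFR values obtained on Day 1". It names no scale, and neither does Protocol 9.4.3.1.3.

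**Group cut-offs.** SAP Table 2 gives the cut-offs in mL/min. Footnote a applies the factor BSA/1.73 and continues: "The average of the 2 unnormalized eGFR values from S1 and S2 will be used for study enrollment and group placement". SAP 6.1.1.1 puts these cut-offs on the clearance plots: "Vertical lines for the renal function group cut-off values will also be presented on the plots".

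**Protocol.** Protocol 4.1 prints the same CKD-EPI equation, then uses each participant's "ratio of BSA/1.73 to obtain the BSA-unnormalized eGFR value as shown below", and supplies the BSA formula. SAP 3.2.1 carries over the equation without these two steps.

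**Alternative equations.** SAP 3.2.1 gives Cockcroft-Gault as "eGFR (ml/min/1.73 m²) = [(140-Age"..., with total weight in kg and no BSA term, and MDRD per 1.73 m². SAP 6.1.1.1 repeats the regressions and figures with each, for exploratory purposes.

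**The concern.** A programmer who follows SAP 6.1.1.1 to SAP 3.2.1 arrives at a value per 1.73 m² and finds no instruction to convert it. The lines drawn on the same axis are in mL/min. A participant with BSA above 1.73 m² then plots to the left of where group placement put them, and one with smaller BSA plots to the right. The slope and intercept are reported in a unit the SAP does not settle.

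These outputs sit in the SAP's main analysis section. They show how clearance changes across the renal-function range, and Protocol 2.3 says the study results will feed dosing recommendations in renal impairment. A plot whose points disagree with its own cut-off lines can be misread.

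The Cockcroft-Gault label is a separate fault with a practical consequence. Anyone who multiplies everything labelled per 1.73 m² by BSA/1.73 would wrongly convert a value already in mL/min.

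**Working it through.** The documents state no figure that depends on this choice, so there is none to reproduce. The check applies their own formulas.

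**Size of the scale factor.** Protocol 4.1 gives BSA = 0.007184 × weight^0.425 × height^0.725. At 90 kg and 170 cm:

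- BSA = 0.007184 × 90^0.425 × 170^0.725 = 2.014 m²
- BSA/1.73 = 1.164
- Cut-offs per 1.73 m²: 90/1.164 = 77.3, 60/1.164 = 51.5, 30/1.164 = 25.8

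| Weight, height | BSA/1.73 | 90/60/30 mL/min expressed per 1.73 m² |
|---|---|---|
| 80 kg, 170 cm | 1.107 | 81/54/27 |
| 90 kg, 170 cm | 1.164 | 77/52/26 |
| 110 kg, 175 cm | 1.295 | 69.5/46.3/23.2 |

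Body sizes checked inside the eligibility limits (BMI 18.0 to <45.4 kg/m², weight >50 kg; Protocol 5.1.1) give ratios from about 0.83 (50.1 kg, 150 cm) to about 1.49 (145 kg, 180 cm).

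**Individual examples (assumed values).**

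- Man, 62 years, SCr 1.35 mg/dL, 110 kg, 175 cm. CKD-EPI = 141 × (1.35/0.9)^-1.209 × 0.993^62 = 55.9 mL/min/1.73 m², in the moderate band. With the BSA step, 55.9 × 1.295 gives 72.3 mL/min, which is mild.
- Woman, 60 years, SCr 1.0 mg/dL, 55 kg, 158 cm. CKD-EPI = 61.2 per 1.73 m² (mild band) against 54.8 mL/min (moderate), so the shift is in the other direction.

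**Share of T2DM points outside their own band, from scale alone.** This was simulated with 400,000 draws per group. Assumptions:

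- weight normal with mean 80, 90 or 100 kg and SD 15, truncated at 50 kg; height normal, 170 cm, SD 9; BMI within the limits
- unnormalised eGFR uniform within each group, with Group 5 at 10-30 and Group 2 from 90 up to 110, 120 or 130 mL/min
- equal group sizes

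| Mean weight | Group 2 to 110 | to 120 | to 130 |
|---|---|---|---|
| 80 kg | 21.7% | 18.0% | 15.9% |
| 90 kg | 29.1% | 24.5% | 21.6% |
| 100 kg | 36.2% | 31.5% | 27.8% |

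At 90 kg the shares by group are 67/48/37% for Group 2, 33% for Group 3, 17% for Group 4 and under 1% for Group 5.

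**Crossing that remains on the right scale.** Groups use the S1/S2 average and plots use Day 1, so some points cross a line regardless. With an assumed within-person CV, at mean weight 90 kg (three Group 2 bounds as above):

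- CV 5%: 8.6/7.6/7.2% in mL/min against 29.4/25.3/22.4% per 1.73 m²
- CV 10%: 17.1/15.3/14.3% against 31.1/27.7/25.0%

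The excess due to scale is 10.7 (25.0 - 14.3) to 20.8 (29.4 - 8.6) percentage points. Dialysis participants, placed in Group 5 whatever their eGFR, add further crossing and were not simulated.

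**Slope.** This was checked with 3,000 simulated trials of n = 32, SD 0.489 on the log scale (Protocol 9.2), and an assumed 2-fold change per 75 mL/min, so slope = ln 2/75 = 0.0092. The ratio of normalised to unnormalised slope is 1.065-1.07 at 80 kg, 1.12-1.13 at 90 kg and 1.17-1.18 at 100 kg. At 90 kg the shift is 0.0011-0.0012 against a 90% CI half-width of 0.0042-0.0047. R² changes by less than 0.01.

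**Cockcroft-Gault.** The printed formula for a 60-year-old man with SCr 1.0 mg/dL gives 80 × 60/72 = 66.7 at 60 kg and 80 × 120/72 = 133.3 at 120 kg. A result that doubles with weight is not normalised to body size. For the 110 kg man above, the formula gives 78 × 110/(72 × 1.35) = 88.3 mL/min; a true per-1.73 m² value would be 88.3/1.295 = 68.2.

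**The case against.** The strongest reply is that the BSA step was intended throughout. SAP 2.2 uses the same pointer for the Table 2 eGFR, saying "the estimate of eGFR will be based on the SCr-based CKD-Epi equation, defined in Section 3.2.1", and there footnote a plainly adds the conversion, so a pointer to 3.2.1 may name the equation without excluding the step. The protocol's eligibility criteria also use plain eGFR for the mL/min value, and cut-off lines that exist only in mL/min suggest an mL/min axis. That intention is plausible. But footnote a belongs to the study-group table and its placement rule, which use S1 and S2. The regression uses a different measurement, Day 1, and its definition leads only to the per-1.73 m² equation.

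The second reply is that little inference depends on it. This is largely right. The ANOVA of Cmax, AUC and fu does not use eGFR, no hypothesis test or decision rule rests on the regression, the slope change is small against its interval, and plot symbols still identify each group.

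The third reply is that the shares rest on assumed body sizes and eGFR distributions, because the documents give none. That also stands. The net excess varies with weight as the gross share does: a rerun with Group 2 weights held within ±15 kg of the mean, as Protocol 5.1.3 requires, gives about 6-14 points at 80 kg and 16-28 at 100 kg.

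The Cockcroft-Gault fault affects a label in an exploratory output, not the computed values. The Appendix 1 variable names are in code offered as an example.

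**Conclusion.** The concern holds. As written, the SAP puts the points on a per-1.73 m² scale and the cut-off lines in mL/min, and it gives Cockcroft-Gault the wrong unit. It should be fixed, but it does not threaten the primary group comparisons or the sample size.

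The visible effect is on the plots. Roughly 16-36% of T2DM points fall outside their own band from scale alone, and at a mean weight of 90 kg the excess over unavoidable Day 1 variation is about 11-21 percentage points. These figures depend on the assumed weights, the within-group eGFR distribution and the within-person CV. The effect on the regression is mainly an ambiguous unit: a slope about 7-18% larger numerically, with almost no change in fit. That the lines are in mL/min is inferred from Table 2, the only place the cut-offs are defined.

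**What to change.** - In SAP 3.2.1, 5.2.4 and 6.1.1.1, state that the regressor and x-axis are Day 1 CKD-EPI eGFR × BSA/1.73 in mL/min, with BSA from the Protocol 4.1 formula and the S1 height and weight.
- Apply the same conversion to MDRD, so that its exploratory plots match the cut-off lines.
- Relabel Cockcroft-Gault as mL/min and state that no BSA step applies.
- Footnote the plots: groups were assigned on the S1/S2 average or on dialysis status, so some Day 1 points may still cross a line.
- As a minor tidy-up of Appendix 1, use the unnormalised CKD-EPI variable in both regression examples in place of `clcr` and `eGFR_cg`, and the ln outcome in both (the second example has `pk_p`).

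The cost is SAP wording and one derived variable. Height and weight are measured at S1 under the Schedule of Activities, and Protocol 5.3.1 provides for predose safety samples on Day 1, so no new data are needed.
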